4.4. End of Study Definition

The end of the study is defined as the date of the last visit of the last participant in the study or last scheduled procedure shown in the [SoA](#) for the last participant in the trial globally.

A participant is considered to have completed the study if they have completed all periods of the study, including the last scheduled procedure shown in the [SoA](#).

5. STUDY POPULATION

This study can fulfill its objectives only if appropriate participants are enrolled. The following eligibility criteria are designed to select participants for whom participation in the study is considered appropriate. All relevant medical and nonmedical conditions should be taken into consideration when deciding whether a particular participant is suitable for this protocol.

Prospective approval of protocol deviations to recruitment and enrollment criteria, also known as protocol waivers or exemptions, is not permitted.

5.1. Inclusion Criteria

Participants are eligible to be included in the study only if all of the following criteria apply:

Age and Sex:

1. Male participants must be 18 to 60 years of age, inclusive, at the time of signing the ICD.

- Refer to [Appendix 4](#) for reproductive criteria for male ([Section 10.4.1](#)) participants.
- 2. Male participants who are overtly healthy as determined by medical evaluation including medical history, physical examination, blood pressure and pulse rate measurement, standard 12-lead ECG, and laboratory tests.

Other Inclusion Criteria:

- 3. BMI of 17.5 to 30.5 kg/m²; and a total body weight >50 kg (110 lb).
- 4. Participants who are willing and able to comply with all scheduled visits, treatment plan, laboratory tests, lifestyle considerations, and other study procedures including collection of blank urine and feces samples prior to dosing on Day 1, Period 1.
- 5. Capable of giving signed informed consent as described in [Appendix 1](#), which includes compliance with the requirements listed in the ICD and in this protocol.

5.2. Exclusion Criteria

Participants are excluded from the study if any of the following criteria apply:

Medical Conditions:

- 1. Evidence or history of clinically significant hematological, renal, endocrine, pulmonary, gastrointestinal, cardiovascular, hepatic, psychiatric, neurological, or allergic disease (including drug allergies, but excluding untreated, asymptomatic, seasonal allergies at the time of dosing).
 - Any condition possibly affecting drug absorption (eg, gastrectomy, cholecystectomy).
 - Positive testing at screening for HIV, HBsAg, HBcAb, HBsAb or HCVAb. Note: A positive HBsAb due to hepatitis B vaccination is permissible.
- 2. Personal or family history of MTC or MEN2, or participants with suspected MTC per the investigator's judgement.
- 3. History of irregular bowel movements (eg, irritable bowel syndrome, frequent episodes of diarrhea, or constipation defined by less than 1 bowel movement on average per 2 days) or lactose intolerance.
- 4. Other medical or psychiatric condition including recent (within the past year of screening) or active suicidal ideation/behavior or laboratory abnormality or other conditions or situations related to COVID-19 pandemic (eg, contact with positive case) that may increase the risk of study participation or, in the investigator's judgment, make the participant inappropriate for the study.

Prior/Concomitant Therapy:

5. Use of any prescription or non-prescription drugs and dietary and herbal supplements as outlined in [Section 6.9](#) and [Appendix 10](#).

Prior/Concurrent Clinical Study Experience:

6. Previous administration with an investigational product (drug or vaccine) within 90 days (or as determined by the local requirement) preceding the first dose of study intervention used in this study.
7. Known prior participation (ie, received at least 1 dose of study intervention) in a study involving PF-07081532 or known intolerance to a GLP-1R agonist.

Diagnostic Assessments:

8. A positive urine drug test at screening or admission.
9. Screening supine BP ≥ 140 mm Hg (systolic) or ≥ 90 mm Hg (diastolic), following at least 5 minutes of supine rest. If BP is ≥ 140 mm Hg (systolic) or ≥ 90 mm Hg (diastolic), the BP should be repeated 2 more times and the average of the 3 BP values should be used to determine the participant's eligibility.
10. eGFR <90 mL/min/1.73m² (calculated with the 2021 CKD-EPI Scr only equation) at screening.
11. Standard 12-lead ECG that demonstrates clinically relevant abnormalities that may affect participant safety or interpretation of study results (eg, QTcF >450 ms, complete LBBB, signs of an acute or indeterminate- age myocardial infarction, ST-T interval changes suggestive of myocardial ischemia, second- or third- degree AV block, or serious bradyarrhythmias or tachyarrhythmias). If the uncorrected QT interval is >450 ms, this interval should be rate-corrected using the Fridericia method only and the resulting QTcF should be used for decision making and reporting. If QTcF exceeds 450 ms, or QRS exceeds 120 ms, the ECG should be repeated twice and the average of the 3 QTcF or QRS values used to determine the participant's eligibility. Computer-interpreted ECGs should be overread by a physician experienced in reading ECGs before excluding a participant.
12. Participants with **ANY** of the following abnormalities in clinical laboratory tests at screening, as assessed by the study-specific laboratory and confirmed by a single repeat test, if deemed necessary:
 - AST **or** ALT level $\geq 1.5 \times$ ULN;

- Total bilirubin level $\geq 1.5 \times$ ULN; participants with a history of Gilbert's syndrome may have direct bilirubin measured and would be eligible for this study provided the direct bilirubin level is \leq ULN.

Other Exclusion Criteria:

13. History of alcohol abuse or binge drinking and/or any other illicit drug use or dependence within 6 months of Screening. Binge drinking is defined as a pattern of 5 (male) or more alcoholic drinks in about 2 hours. As a general rule, alcohol intake should not exceed 14 units per week (1 unit = 8 ounces [240 mL] beer, 1 ounce [30 mL] of 40% spirit, or 3 ounces [90 mL] of wine).
14. Blood donation (excluding plasma donations) of approximately 1 pint (500 mL) or more within 60 days prior to dosing.
15. History of sensitivity to heparin or heparin-induced thrombocytopenia *only if* heparin is planned to flush IV catheters.
16. Total [^{14}C] radioactivity measured in plasma at screening exceeding 11 mBq/mL.
17. Participants with current use of tobacco- and/or nicotine-containing products exceeding equivalent of 5 cigarettes per day.
18. Investigator site staff directly involved in the conduct of the study and their family members, site staff otherwise supervised by the investigator, and sponsor and sponsor delegate employees directly involved in the conduct of the study and their family members.

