the informed consent is not withdrawn prior to participating in any study activity after screening. Potential participants who are screened for the purpose of determining eligibility for the study, but do not participate in the study, are not considered enrolled, unless otherwise specified by the protocol.

Study Population:

Inclusion and exclusion criteria are listed below:

Inclusion Criteria

Participants must meet the following inclusion criteria to be eligible for enrollment into the study:

1. Male participants must be 18 to 60 years of age, inclusive, at the time of signing the ICD.
2. Male participants who are overtly healthy as determined by medical evaluation including medical history, physical examination, blood pressure and pulse rate measurement, standard 12-lead ECG, and laboratory tests.
3. BMI of 17.5 to 30.5 kg/m²; and a total body weight >50 kg (110 lb).
4. Participants who are willing and able to comply with all scheduled visits, treatment plan, laboratory tests, lifestyle considerations, and other study procedures including collection of blank urine and feces samples prior to dosing on Day 1, Period 1.
5. Capable of giving signed informed consent, which includes compliance with the requirements listed in the ICD and in this protocol.

Exclusion Criteria

Participants with any of the following characteristics/conditions will be excluded:

1. Evidence or history of clinically significant hematological, renal, endocrine, pulmonary, gastrointestinal, cardiovascular, hepatic, psychiatric, neurological, or allergic disease (including drug allergies, but excluding untreated, asymptomatic, seasonal allergies at the time of dosing).
 - Any condition possibly affecting drug absorption (eg, gastrectomy, cholecystectomy).
 - Positive testing at screening for HIV, HBsAg, HBcAb, HBsAb or HCVAb. Note: A positive HBsAb due to hepatitis B vaccination is permissible.
2. Personal or family history of MTC or MEN2, or participants with suspected MTC per the investigator's judgement.

3. History of irregular bowel movements (eg, irritable bowel syndrome, frequent episodes of diarrhea, or constipation defined by less than 1 bowel movement on average per 2 days) or lactose intolerance.

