8. STUDY ASSESSMENTS AND PROCEDURES

8.1. Administrative Procedures

The investigator (or an appropriate delegate at the investigator site) must obtain a signed and dated ICD before performing any study-specific procedures.

Study procedures and their timing are summarized in the [SoA](#). Protocol waivers or exemptions are not allowed.

Adherence to the study design requirements, including those specified in the [SoA](#), is essential and required for study conduct.

All screening evaluations must be completed and reviewed to confirm that potential participants meet all eligibility criteria. The investigator will maintain a screening log to record details of all participants screened and to confirm eligibility or record reasons for screening failure, as applicable.

Participants will be screened within 28 days prior to administration of the study intervention to confirm that they meet the study population criteria for the study. If the time between screening and dosing exceeds 28 days as a result of unexpected delays (eg, delayed drug shipment), then participants do not require rescreening if the laboratory results obtained prior to first dose administration meet eligibility criteria.

Every effort should be made to ensure that protocol-required tests and procedures are completed as described. However, it is anticipated that from time to time there may be circumstances outside the control of the investigator that make it unfeasible to perform the test. In these cases, the investigator must take all steps necessary to ensure the safety and well-being of the participant. When a protocol-required test cannot be performed, the investigator will document the reason for the missed test and any corrective and preventive actions that they have taken to ensure that required processes are adhered to as soon as possible. The study team must be informed of these incidents in a timely manner.

ECGs and vital sign assessments (pulse rate and BP) should be collected prior to any blood draw. If an IV catheter is utilized for blood sample collections, ECGs and vital sign assessments (pulse rate and BP) should be collected prior to the insertion of the catheter.

For samples being collected and shipped, detailed collection, processing, storage, and shipment instructions and contact information will be provided to the investigator site prior to initiation of the study.

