8.3.4. Clinical Safety Laboratory Assessments

See [Appendix 2](#) for the list of clinical safety laboratory tests to be performed and the [SoA](#) for the timing and frequency. All protocol-required laboratory assessments, as defined in [Appendix 2](#), must be conducted in accordance with the laboratory manual and the [SoA](#). Unscheduled clinical laboratory measurements may be obtained at any time during the study to assess any perceived safety issues.

The investigator must review the laboratory report, document this review, and record any clinically significant changes occurring during the study in the AE section of the CRF. Clinically significant abnormal laboratory test findings are those that are not associated with the underlying disease, unless judged by the investigator to be more severe than expected for the participant's condition.

All laboratory tests with values considered clinically significant and abnormal during participation in the study or within 5 days after the last dose of study intervention should be repeated until the values return to normal or baseline or are no longer considered clinically significant by the investigator or study medical monitor.

If such values do not return to normal/baseline within a period of time judged reasonable by the investigator, the etiology should be identified and the sponsor notified.

See [Appendix 6](#) for suggested actions and follow-up assessments in the event of potential DILI.

See [Appendix 7](#) for instructions for laboratory testing to monitor kidney function and reporting laboratory test abnormalities.

Participants may undergo random urine drug testing at the discretion of the investigator. Drug testing conducted prior to dosing must be negative for participants to receive study intervention.

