9.3.3.2. Safety Analyses

All safety analyses will be performed on the safety population.

AEs, ECGs, BP, pulse rate, and safety laboratory data will be reviewed and summarized on an ongoing basis during the study to evaluate the safety of participants. Any clinical laboratory, ECG, BP, and pulse rate abnormalities of potential clinical concern will be described. Safety data will be presented in tabular and/or graphical format and summarized descriptively, where appropriate.

Medical history and physical examination and neurological examination information, as applicable, collected during the course of the study, will be considered source data and will not be required to be reported, unless otherwise noted. However, any untoward findings identified on physical and/or neurological examinations conducted during the active collection period will be captured as AEs, if those findings meet the definition of an AE. Data collected at screening that are used for inclusion/exclusion criteria, such as laboratory data, ECGs, and vital signs, will be considered source data, and will not be required to be reported, unless otherwise noted. Demographic data and [¹⁴C] measurements collected at screening will be reported.

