10.2. Appendix 2: Clinical Laboratory Tests

The following safety laboratory tests will be performed at times defined in the **SoA** section of this protocol. Additional laboratory results may be reported on these samples as a result of the method of analysis or the type of analyzer used by the clinical laboratory, or as derived from calculated values. These additional tests would not require additional collection of blood. Unscheduled clinical laboratory measurements may be obtained at any time during the study to assess any perceived safety issues.

Table 3. Protocol-Required Safety Laboratory Assessments

Hematology	Chemistry	Urinalysis	Other
Hemoglobin	BUN	pH	Other tests as part of clinical laboratory tests:
Hematocrit	Creatinine (Scr)	Glucose (qual)	COVID-19 test ^f
RBC count	Cystatin C (Scys) on Day -1 only	Protein (qual)	
MCV	eGFR ^a	Blood (qual)	
MCH	Serum Glucose (fasting)	Ketones	At screening only:
MCHC	Calcium	Nitrites	• Serology: HBsAg, HCVAb (if positive, HCV RNA) and HIV
Platelet count	Sodium	Leukocyte esterase	At screening and Day -1 only:
WBC count	Potassium	Urobilinogen	• Urine drug test ^g
Total neutrophils (Abs)	Chloride	Urine bilirubin	
Eosinophils (Abs)	Total CO ₂ (Bicarbonate)	Microscopy ^e	For suspected DILI:
Monocytes (Abs)	AST		• AST, ALT
Basophils (Abs)	ALT		• T bili, direct and indirect bilirubin
Lymphocytes (Abs)	Alkaline phosphatase		• Total bile acids, GGT
	GGT		• Albumin
	T bili		• Alkaline phosphatase
	Direct bilirubin ^{b,c}		• CK
	Indirect bilirubin ^{b,c}		• PT, INR
	Creatine kinase ^{b,d}		• Acetaminophen/paracetamol or protein adduct levels
	Uric acid		
	Albumin		For suspected DICI/DIKI:
	Total protein		Creatinine (Scr)
			Cystatin C (Scys) ^h
			eGFR ^h
			UACR

- a. eGFR should be calculated using the 2021 CKD-EPI Scr only equations, see [Appendix 7](#).
- b. At screening and Day -1 **only**, unless conditions for testing are met after Day 1 per notes “c” and “d” below.
- c. After Day 1, direct and indirect bilirubin assessed only when T bili is > ULN.
- d. After Day 1, creatine kinase assessed only when ALT is > ULN.
- e. If abnormal urine dipstick results including positive results for blood, protein, nitrites or leukocyte esterase.
- f. Assessment of risk for, symptoms of or testing for COVID-19 may be performed at screening, admission to the CRU and/or at other times during the study at investigator discretion and according to local site policies.

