F _h	fraction escaping hepatic first-pass elimination
FU	follow-up
GCP	Good Clinical Practice
GGT	gamma-glutamyl transferase
GLP-1	glucagon-like peptide-1
GLP-1R	glucagon-like peptide-1 receptor
HBcAb	hepatitis B core antibody
HBsAb	hepatitis B surface antibody
HBsAg	hepatitis B surface antigen
HCVA _b	hepatitis C antibody
HIV	human immunodeficiency virus
HR	heart rate
IB	Investigator's Brochure

Abbreviation	Term
ICD	informed consent document
ICH	International Council for Harmonisation of Technical Requirements for Pharmaceuticals for Human Use
ID	identification
IMP	investigational medicinal product
IND	Investigational New Drug
INR	international normalized ratio
IRB	Institutional Review Board
IV	intravenous(ly)
K ₂ EDTA	dipotassium ethylenediaminetetraacetic acid
KDIGO	Kidney Disease Improving Global Outcomes
LBBB	left bundle branch block
LC/MS/MS	liquid chromatography tandem mass spectrometric method
LFT	liver function test
MCH	mean corpuscular hemoglobin
MCHC	mean corpuscular hemoglobin concentration
MCV	mean corpuscular volume
MEN2	multiple endocrine neoplasia type 2
MIST	Metabolites in Safety Testing
MQI	medically qualified individual
MRT	mean residence time
MTC	medullary thyroid carcinoma
NA	not applicable
NIMP	noninvestigational medicinal product
NOAEL	no-observed-adverse-effect level
OATP	organic anion transporting polypeptide
PD	protocol deviation
PE	physical exam
PK	pharmacokinetic(s)
PO	oral(ly)
PPI	proton pump inhibitor
PSSA	Pfizer's Serious Adverse Event Submission Assistant
PT	prothrombin time
PVC	premature ventricular contraction/complex
QD	once daily
QP	qualified person
QTc	corrected QT interval
QTcF	QTc corrected using Fridericia's formula
qual	qualitative
RBC	red blood cell
SAE	serious adverse event
SAI	site administration instructions

Abbreviation	Term
SAP	Statistical Analysis Plan
SARS-CoV-2	severe acute respiratory syndrome coronavirus 2
Scr	serum creatinine
Scys	serum cystatin C
SoA	schedule of activities
SOC	system organ class
SOP	standard operating procedure
SRSD	Single Reference Safety Document
SSID	study-specific participant identification
SUSAR	Suspected Unexpected Serious Adverse Reaction
$t_{1/2}$	plasma elimination half life
T2DM	type 2 diabetes mellitus
TA	Technical Agreement
T bili	total bilirubin
TEAE	treatment-emergent adverse event
THC	tetrahydrocannabinol
T_{max}	time to reach C_{max}
UACR	urine albumin/creatinine ratio
UGT	uridine 5'-diphospho-glucuronosyltransferase
ULN	upper limit of normal

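### Does it matter that Table 3 lists only three of the five serology markers named in exclusion 1?

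*Protocol*

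**What the plan says.** Exclusion 1 appears in the same form in the Synopsis (Section 1.1) and in Section 5.2. It covers "Positive testing at screening for HIV, HBsAg, HBcAb, HBsAb or HCVAb" and adds one exception: "A positive HBsAb due to hepatitis B vaccination is permissible".

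Section 8.3.4 refers to Appendix 2 "for the list of clinical safety laboratory tests to be performed". In that appendix, Table 3 has an entry for tests done at screening only, which reads "Serology: HBsAg, HCVAb (if positive, HCV RNA) and HIV".

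The two markers absent from that entry appear elsewhere only in the abbreviation list (Appendix 11), where HBcAb, for example, is spelled out as "hepatitis B core antibody". The visible text of the Schedule of Activities has a general clinical laboratory row and no separate serology row.

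On screening as a whole, Section 8.1 states: "All screening evaluations must be completed and reviewed to confirm that potential participants meet all eligibility criteria". The SAP does not mention serology.

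**The concern.** The criterion depends on a positive result obtained at screening. If a test is not run it cannot be positive, and that part of the exclusion has no force. Table 3 has a line set aside for screening serology, and that line names three markers from this same criterion, so a reader could reasonably take it as the full panel. A site that did so would run HBsAg, HCVAb and HIV and stop. A man who is HBcAb-positive and HBsAg-negative would then be enrolled although exclusion 1 rules him out.

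At stake would be uniform application of an eligibility rule in a study of about 6 healthy men. If such men differed in how they handle the drug, a few of them could matter in so small a sample.

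**Working it through.** No sample size, error rate or estimate is involved. The check is a comparison of two lists, followed by a trace of where the missing items could enter an analysis.

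**Step 1: compare the lists.**

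| Marker | Exclusion 1 (Synopsis, Section 5.2) | Table 3, screening serology |
|---|---|---|
| HIV | yes | yes |
| HBsAg | yes | yes |
| HCVAb | yes | yes |
| HBcAb | yes | no |
| HBsAb | yes | no |

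Five markers less three leaves two. HCV RNA is run only when HCVAb is positive, so it is not a fourth marker. The serology entry in Table 3 is intact, with no sign of redaction or broken text.

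**Step 2: does anything else in the protocol supply the two tests?** The abbreviation list orders nothing. The hepatitis testing in Appendix 6 belongs to the work-up of suspected liver injury. The allowance in Appendix 2 for extra results is permissive and covers by-products of the assay method or analyzer. That leaves two routes:

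- Exclusion 1 presupposes a screening result for each marker it names, and Section 8.1 requires the screening evaluations to confirm all criteria. Read together, these call for whatever results the criteria need.
- Section 8.3.4 says that the required assessments follow the laboratory manual as well as the Schedule of Activities. The manual is not among the documents and may specify the hepatitis B panel.

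**Step 3: is Table 3 meant to hold every eligibility assay?** It is presented as a list of safety laboratory assessments, and it is not complete for eligibility. Exclusion 16 turns on "radioactivity measured in plasma at screening exceeding 11 mBq/mL", and that assay is not in Table 3 either. It is nevertheless done: Section 9.3.3.2 states that [14C] "measurements collected at screening will be reported". Absence from Table 3 therefore does not by itself show that a test is not performed.

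**Step 4: if the two assays were skipped, what would change in the results?**

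- Section 9.3.3.2 treats screening laboratory data used for eligibility as source data that normally need not be reported. Serology therefore need not enter the reported data at all.
- The SAP's mixed model (Section 5.2.3) has treatment as a fixed effect and participant as a random effect, with no covariates. SAP Section 6.4 plans no subset analyses, and the demographic summary in SAP Section 6.5.1 does not include serology.
- F compares oral and IV exposure in the same man within Period 2. F_a compares urinary recovery in the same man across the two periods. A stable trait of a participant is present on both sides of each ratio. It does not have to cancel: the protocol notes that F depends in part on hepatic first pass. But it does not favour one route through who was enrolled.
- Total recovery and metabolite profiling are descriptive in Period 1. The extent of excretion set already leaves out participants with protocol deviations that may have affected that analysis (Protocol Section 9.2, SAP Section 4), so an ineligible participant found later can be dealt with there.
- Other liver-related safeguards still apply: HBsAg and HCVAb serology, the exclusion for clinically significant hepatic disease, and the limits of 1.5 times the upper limit of normal on AST, ALT and total bilirubin in exclusion 12.

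**The case for a change.** The strongest case for acting is that Section 8.1 names no assay. A site has to notice for itself that the required panel falls short of the criterion, and a line devoted to screening serology invites the opposite reading. The [14C] comparison is also imperfect: another section confirms that [14C] is measured at screening, and nothing does the same for HBcAb or HBsAb. Even if the laboratory manual names both tests, the protocol's two lists would still differ. All of this stands, and it establishes a drafting inconsistency.

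Two further arguments add nothing separate. The vaccination exception does need an HBsAb result, but it serves only to excuse a positive one; where HBsAb is not measured there is nothing to excuse. The ban on waivers in Section 5 concerns approving known departures from enrolment criteria in advance. A site that does not run an assay missing from Table 3 is not granting a waiver.

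What the case for acting does not supply is a consequence. It identifies no endpoint, interval, analysis set or safety assessment that would come out differently.

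**Conclusion.** The mismatch is real and small: Table 3 omits 2 of the 5 serology markers in exclusion 1. It does not make the criterion unworkable, because the criterion itself together with Section 8.1 gives a site the basis for obtaining both results. If a site ran only the three listed tests, the mass-balance, metabolite, F, F_a and safety conclusions would still be sound on everything the documents show.

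This rests on two assumptions. The first is that sites read the eligibility criteria alongside Table 3, or that the laboratory manual names the assays; the manual could not be checked. The second is that the remaining hepatic criteria are applied as written.

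The point is a clerical omission from a table. The sponsor may align the two lists whenever the text is next revised, and which list stands is the sponsor's decision. Keeping three markers would be an edit of wording, while keeping five would add two assays to the listed screening tests. Neither the design nor the analysis depends on that choice.
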